7. Has not had an acute illness as determined by study clinician licensed to make medical diagnoses and listed on the Form FDA 1572, within 72 hours prior to vaccination.
 - a. An acute illness which is nearly resolved with only minor residual symptoms remaining is allowable if, in the opinion of the site PI or appropriate sub-investigator, the residual symptoms will not interfere with the ability to assess safety parameters as required by the protocol.
8. Has not had a new or prior unsolicited AE, unrelated to study product, that is more than Grade 2 at the time of vaccination.
9. Has not had a new unsolicited AE related to study product that is greater than Grade 1 at the time of vaccination.
10. Has not had a prior unsolicited AE related to study product persisting at the time of vaccination and is greater than Grade 1.
11. Has not had a new solicited AE related to study product that is greater than Grade 1 at the time of vaccination.
12. Has not had a prior solicited AE related to study product persisting at the time of vaccination and is greater than Grade 1.
13. In the judgement of the PI does not have any other contraindication to dosing.

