5.3.3 Subsequent Vaccination Visits: Day 29 (+2) and Day 57 (+2)

All subjects in each cohort will return on Day 29 (Visit 05) and Day 57 (Visit 09) after vaccination 1 and undergo the following procedures:

- Qualification criteria for subsequent vaccination visits, will be reviewed prior to vaccination. [Section 4.1.3](#)
- Interim medical history, including an assessment for new medical conditions, stability of chronic diseases, MAAEs, NOCMCs and symptoms suggestive of PIMMCs, will be obtained by interview of subjects prior to study vaccination. Any changes in medical history since the screening visit will be reviewed to ensure subjects continue to qualify for vaccination.

- Concomitant medications will be reviewed with subjects prior to study vaccination for accuracy and completeness. Any new concomitant medications will be reviewed to ensure subjects continue to qualify for vaccination.
- Vital signs, including oral temperature, pulse, and BP, will be obtained prior to study vaccination to ensure subjects continue to qualify for vaccination. Subjects must not eat or drink anything hot or cold, or smoke within 10 minutes prior to taking oral temperature.
- If indicated after review of subject history, a targeted physical examination may be performed prior to study vaccination.
- For all participants of childbearing potential, a urine pregnancy test will be performed within 24 hours of vaccination. Results must be negative and known prior to study vaccination.
- Pre-vaccination reactogenicity assessments will be completed
- Venous blood will be collected immediately prior to study vaccination for:
 - Serum for Serology
 - PBMC for secondary research
 - Serum for secondary research
- Subjects will receive one dose of study vaccine via a single IM injection into the deltoid muscle of the subject's arm. It is strongly recommended the unblinded administrator alternate the subject's arms for injections. The site of injection (right or left arm) and time of study vaccine administration to the subject will be recorded on the appropriate eCRF.
- Subjects will be observed in the clinic for at least 30 minutes after study vaccination. The study vaccination site will be examined, post-administration reactogenicity assessments will be performed, and any AE/SAEs will be recorded on the appropriate eCRF prior to discharge from the clinic.

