#### 3.2. Endpoints

##### Primary

- Occurrence of solicited local and systemic AEs through 7 days after each study vaccination
- Occurrence of vaccine-related unsolicited AEs through 28 days post last vaccination
- Occurrence of serious adverse events (SAEs) through approximately 12 months post last vaccination
- Occurrence of medically attended adverse events (MAAEs), new-onset chronic medical conditions (NOCMCs), and potentially immune-mediated medical conditions (PIMMCs) from the time of the first study vaccination through approximately 12 months (or throughout the period of their study participation) following the last vaccination

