### 3.3. Study Definitions and Derived Variables

Unless otherwise specified, the baseline value will be defined as the last value obtained prior to the first vaccination. Vital signs assessed on Day 1 prior to study vaccination will be considered as baseline. Any medical condition that is present at the time that the participant is screened will be considered as baseline and will only be reported as an AE if symptoms related to the condition occur with greater frequency and/or severity after vaccination during the AE reporting period.

Change from baseline is defined as the additive change from baseline, i.e.,  $CHG_{ij} = y_{ij} - y_{i0}$  where  $y_{ij}$  is the measurement for participant  $i$  at time point  $j$  and  $y_{i0}$  is the measurement for participant  $i$  at baseline (prior to vaccination 1).

Fold-rise (FR) from baseline is defined as the multiplicative change from baseline, i.e.,  $FR_{ij} = \frac{y_{ij}}{y_{i0}}$  where  $y_{ij}$  is the response for participant  $i$  at time point  $j$  and  $y_{i0}$  is the response for participant  $i$  at baseline (pre-vaccination 1). Individual FR values will be reported to 1 decimal place.

The peak titer and peak fold-rise are defined as the maximum value for a participant at any time after the first vaccination.

A responder is defined as having  $\geq 4$ -fold increase relative to baseline, i.e.,  $FR_{ij} \geq 4$  for participant  $i$  at post-baseline time point  $j$ . For serum assays, participants are classified as responders or not at Days 8, 29, 36, 57, 64, 85, and 113; for the ALS assay, participants are classified as responders or not at Days 8, 36, and 64.

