  - Unexpected event means an event unforeseen by the researcher or the participant, in terms of nature, severity, or frequency, and is not listed in the Investigator's Brochure, package insert, and/or summary of product characteristics.
- At least possibly related to the study product.

NOCMCs are defined as any new ICD-10 diagnosis that is applied to the participant during the duration of the study, after receipt of the study agent, that is expected to continue for at least 3 months and requires continued health care intervention.

MAAEs are any unsolicited AE for which a participant received medical attention, defined as hospitalization, an ER visit, or an otherwise unscheduled visit to or from medical personnel.

PIMMCs constitute a group of AEs that includes diseases which are clearly autoimmune in etiology and other inflammatory and/or neurologic disorders which may or may not have autoimmune etiologies. A list of qualifying conditions is in Appendix C of the protocol [v6.0, 08MAY2023].

Any medical condition that is present at the time that the participant is screened will be considered as baseline and not reported as an AE. However, if the severity of any pre-existing medical condition increases, it should be recorded as an AE.

Solicited adverse events are AEs that are common and known or expected to occur following the administration of the study product. Participants will be assessed for solicited AEs prior to and 30 minutes after each vaccine administration prior to the participant leaving the clinic. On the day of vaccination, participants will receive a thermometer and instructions to complete an e-memory aid to record symptoms for 7 days following each vaccination. The participant e-memory aid will be reviewed with the participant at study visits 48 hours and 7 days after each vaccination (Study Visits 02, 03, 06, 07, 10, and 11). Any symptoms still present after the solicited event collection period (Study Days 1-8 for first vaccination, Study Days 29-36 for second vaccination, and Study Days 57-64 for third vaccination) will continue to be followed until resolution or determined to be stable per investigator. Solicited events will be graded using the Toxicity Grading Scales in [Table 5](#); for quantitative measurements of local injection site reactions, the grading scale classifications of "Small", "Medium", and "Large" will be presented as "Mild", "Moderate", and "Severe" respectively for consistency with other AEs.

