## Vital Signs

Per the MOP Appendix B, vital signs that meet the protocol-defined toxicity grading scale ([Table 6](#)) and represent a worsening condition from baseline are reported as an unsolicited AE with the exception of temperatures collected from the time of vaccination through 7 days post vaccination for each vaccination which will be reported as solicited AEs.

The last measurement prior to receiving the first vaccination for each parameter will be considered baseline.

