### 9.3.1.     Solicited Events and Symptoms

Temperatures collected on the Vital Signs eCRF within 7 days following vaccination will be considered towards the solicited AE of fever and will be included in all tables, figures, and listings summarizing solicited AEs.

The number and percentage with 95% CI of participants reporting at least one solicited adverse event of at least mild severity within 7 days following vaccination will be summarized for each solicited symptom, any systemic symptom, any local symptom, and any symptom following each vaccination and following any vaccination for Cohort 1 ([Table 32](#)), Cohort 2 ([Table 33](#)), and Cohort 3 ([Table 34](#)). The 95% CI will be calculated using Clopper-Pearson methodology from a binomial distribution (SAS Proc Freq with a binomial option).

For each systemic and local symptom, any systemic symptom, any local symptom, and any solicited symptom, the number and percentage of participants reporting the symptom will be summarized by severity for each day and maximum severity within 7 days after each vaccination for Cohort 1 for vaccination 1 ([Table 35](#)), vaccination 2 ([Table 36](#)), vaccination 3 ([Table 37](#)), and any vaccination ([Table 38](#)). Analogous tables for each vaccination and any vaccination will be presented for Cohort 2 ([Table 39](#), [Table 40](#), [Table 41](#), and [Table 42](#)) and Cohort 3 ([Table 43](#), [Table 44](#), [Table 45](#), and [Table 46](#)). For each event the denominator is the number of participants with non-missing data for the specific event.

The percentage of participants reporting any solicited systemic symptom will be summarized graphically in a bar chart by maximum severity, day post vaccination, and vaccination group for each vaccination ([Figure 32](#), [Figure 33](#), and [Figure 34](#)) and for all vaccinations combined ([Figure 35](#)). Analogous figures will be presented for any solicited local symptom ([Figure 36](#), [Figure 37](#), [Figure 38](#), and [Figure 39](#)).

The percentage of participants experiencing each solicited symptom within 7 days of vaccination will be summarized in a bar chart by maximum severity and treatment group for each vaccination ([Figure 40](#), [Figure 41](#), and [Figure 42](#)) and for all vaccinations combined ([Figure 43](#)).

All solicited adverse events will be presented by participant in [Listing 9](#) for systemic symptoms and [Listing 10](#) for local symptoms.

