[Etc.]	[Etc.]																							
Other (Non-serious) Adverse Events – Non-systematic Collection																								
All	All	x	x	x	x	x	x	x	x	x	x	x	x	x	x	x	x	x	x	x	x	x	x	x
[PT 1]	[SOC 1]	x	x	x	x	x	x	x	x	x	x	x	x	x	x	x	x	x	x	x	x	x	x	x
[Etc.]	[Etc.]																							
Other (Non-serious) Adverse Events – Systematic Collection																								
All	All	x	x	x	x	x	x	x	x	x	x	x	x	x	x	x	x	x	x	x	x	x	x	x
[PT 1]	[SOC 1]	x	x	x	x	x	x	x	x	x	x	x	x	x	x	x	x	x	x	x	x	x	x	x

Preferred Term	MedDRA System Organ Class	1 µg CJCV2 (N=X)			1 µg CJCV2+ALFQ (N=X)			3 µg CJCV2 (N=X)			3 µg CJCV2+ALFQ (N=X)			10 µg CJCV2 (N=X)			10 µg CJCV2+ALFQ (N=X)			All Participants (N=X)			
		n	%	Events	n	%	Events	n	%	Events	n	%	Events	n	%	Events	n	%	Events	n	%	Events	
[Etc.]	[Etc.]																						

Notes: N = Number of participants in the Safety Population (number of participants at risk); Events = Total frequency of events reported.  
Participants can only be counted once per PT.  
a All SAEs are included in the table; a listing of Serious Adverse Events is included in Section 14.3.2.

**14.3.1.1      Solicited Adverse Events****Table 32:      Number and Percentage of Participants Experiencing Solicited Events with 95% Confidence Intervals by Symptom, Vaccination, and Treatment Group - Cohort 1**

*[Implementation Note: This table will summarize all post-vaccination solicited symptoms of at least mild severity regardless of pre-vaccination severity.]*

Symptom	Vaccination a	1 µg CJC2				1 µg CJC2+ALFQ			
		N	n	%	95% CI b	N	n	%	95% CI b
Any Solicited Symptom	Vac 1	x	x	xx	xx, xx	x	x	xx	xx, xx
	Vac 2	x	x	xx	xx, xx	x	x	xx	xx, xx
	Vac 3	x	x	xx	xx, xx	x	x	xx	xx, xx
	Any Vac	x	x	xx	xx, xx	x	x	xx	xx, xx
Systemic Symptoms									
Any Systemic Symptom	Vac 1	x	x	xx	xx, xx	x	x	xx	xx, xx
	Vac 2	x	x	xx	xx, xx	x	x	xx	xx, xx
	Vac 3	x	x	xx	xx, xx	x	x	xx	xx, xx
	Any Vac	x	x	xx	xx, xx	x	x	xx	xx, xx
Arthralgia	Vac 1	x	x	xx	xx, xx	x	x	xx	xx, xx
	Vac 2	x	x	xx	xx, xx	x	x	xx	xx, xx
	Vac 3	x	x	xx	xx, xx	x	x	xx	xx, xx
	Any Vac	x	x	xx	xx, xx	x	x	xx	xx, xx
Fatigue	Vac 1	x	x	xx	xx, xx	x	x	xx	xx, xx
	Vac 2	x	x	xx	xx, xx	x	x	xx	xx, xx
	Vac 3	x	x	xx	xx, xx	x	x	xx	xx, xx
	Any Vac	x	x	xx	xx, xx	x	x	xx	xx, xx
Fever	Vac 1	x	x	xx	xx, xx	x	x	xx	xx, xx
	Vac 2	x	x	xx	xx, xx	x	x	xx	xx, xx
	Vac 3	x	x	xx	xx, xx	x	x	xx	xx, xx
	Any Vac	x	x	xx	xx, xx	x	x	xx	xx, xx
Feverishness c	Vac 1	x	x	xx	xx, xx	x	x	xx	xx, xx
	Vac 2	x	x	xx	xx, xx	x	x	xx	xx, xx

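### Systemic solicited-AE rates in SAP Tables 32–34 include symptoms already present before the dose, and no planned summary row separates them

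*SAP*

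**What the plan says.** The first primary endpoint (SAP 3.2; Protocol 2.3) is "Occurrence of solicited local and systemic AEs through 7 days after each study vaccination". SAP 9.3.1 turns this into the number and percentage of participants with "at least one solicited adverse event of at least mild severity within 7 days following vaccination", with exact confidence intervals, in Tables 32–34. It sets no pre-dose condition, and the implementation note to Table 32 makes that explicit: "This table will summarize all post-vaccination solicited symptoms of at least mild severity regardless of pre-vaccination severity". The footnote to Table 35, which also serves Tables 36–46, defines Maximum as the highest severity reported in the 7 days after the dose, again without reference to the pre-dose grade.

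The pre-dose grade is collected. SAP 4.5.1 says: "Participants will be assessed for solicited AEs prior to and 30 minutes after each vaccine administration". Protocol 5.3.3 repeats this for Days 29 and 57: "Pre-vaccination reactogenicity assessments will be completed". The Table 35 footnote limits the pre-vaccination assessment to systemic symptoms.

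Mild symptoms may be present when doses 2 and 3 are given. One qualification criterion in Protocol 4.1.3 reads: "Has not had a prior solicited AE related to study product persisting at the time of vaccination and is greater than Grade 1". A Grade 1 reaction therefore does not block dosing. The same section also tolerates minor residue of a nearly resolved illness, and unrelated unsolicited events up to Grade 2.

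**The concern.** A participant with a mild headache before the injection who still has it 30 minutes later is counted in Tables 32–34 as having a solicited event of that dose. SAP 4.2 states that there is no placebo. For the absolute rate in an arm, such as systemic symptoms after 10 µg CJCV2 alone, the participant's own pre-dose grade is therefore the only planned measurement that can show that a symptom came before the vaccine. The incidence tables do not use it.

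Elsewhere the SAP does compare with baseline. A condition present at screening "will only be reported as an AE if symptoms related to the condition occur with greater frequency and/or severity after vaccination" (3.3). Graded vital signs that "represent a worsening condition from baseline are reported as an unsolicited AE" (4.5.1, Vital Signs). These rules are not the same as a per-dose reactogenicity rule, but they show that the idea is already in the plan.

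What is at stake is how the absolute and per-dose systemic rates of a primary endpoint are read, in groups where one participant is worth 10 percentage points.

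**Working it through.** **Inputs.** Ten participants per group and a stated exact 95% CI of 0–31% for no events (SAP section 5; Protocol 9.2). Three doses, 28 days apart. ALFQ systemic reactions described as lasting 24–36 hours (Protocol 3.1.2). Temperature below 100.4°F required at entry and at doses 2 and 3 (Protocol 4.1.1, 4.1.3). The probability b that a participant has a systemic symptom before a dose which is still present afterwards is **not in the documents**; I use an assumed range of 2% to 30%.

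**Step 1: reproduce the plan's figure.** The Clopper-Pearson upper limit for 0/10 is 1 − 0.025^(1/10) = 30.8%, which rounds to the stated 31%.

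**Step 2: the effect of a few participants.** Suppose no one has a new or worsened symptom and x of 10 have a persisting pre-dose symptom. The planned rule reports:

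- x = 1: 10% (0.3–44.5%)
- x = 2: 20% (2.5–55.6%)
- x = 3: 30% (6.7–65.2%)

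A new-or-worsened rule would report 0/10 (0–31%) each time. This step needs no assumption about b.

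**Step 3: how often this could happen, under assumed b.** The chance that at least one of 10 is counted for a pre-dose symptom at one dose is 1 − (1−b)^10. If pre-dose symptoms are independent across doses and always persist, the any-vaccination rate with no vaccine effect at all is 1 − (1−b)^3.

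| assumed b | at least 1 of 10, one dose | any-vaccination rate, no vaccine effect |
|---|---|---|
| 2% | 18% | 6% |
| 5% | 40% | 14% |
| 10% | 65% | 27% |
| 20% | 89% | 49% |
| 30% | 97% | 66% |

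**Step 4: the ALFQ comparison.** Let v be the vaccine-induced rate, independent of b, for one symptom and with no worsening of a pre-existing one. The planned rule gives 1 − (1−b)(1−v); a new-onset rule gives (1−b)v. The arm difference is (1−b)(v₁ − v₀) under both. With b = 10%, v₀ = 20% and v₁ = 60%, the planned rule shows 28% and 64%, and a new-onset rule shows 18% and 54%. Both differences are 36 points, against a true 40. With v = 0 in both arms, the planned rule shows 10% in each and no difference.

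**Step 5: which rows are exposed.** Mild fever starts at 100.4°F, so fever cannot be present at dosing. Local symptoms have no pre-vaccination grade in the tables. Carry-over of a reaction from one dose to the next would need it to last about 28 days. It could affect only the Vac 2 and Vac 3 rows, because the participant is already counted under Any Vac from the earlier dose. What remains is the systemic symptoms other than fever, plus the summary rows that contain them.

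**The case against.** The strongest defence is that the rule is explicit, disclosed and faithful to the endpoint, which asks for occurrence after each dose with no baseline or relatedness condition. Counting everything errs on the cautious side in a first-in-human trial. That stands, and it is why the current rows should stay.

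The second defence is that nothing is hidden. A reader might infer that the pre-dose information cannot be recovered, because the pre-vaccination rows in Tables 35–46 are marginal counts by arm that cannot be linked to post-dose grades. The documents do not support that. Listing 9 includes pre- and post-vaccination assessments by participant, dose, day and symptom, and shows events that outlast Day 8 under the vaccination they followed. With about 10 per arm the link can be made by hand. The gap is in the summary tables.

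A reader might also infer that the rule distorts the ALFQ comparison. CJCV2 alone is a randomised, blinded, concurrent comparator within each cohort, so pre-dose symptoms fall on both arms equally in expectation. The shrinkage by (1−b) in step 4 is the same under a new-onset rule, so it is no argument for changing the rule.

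Nor do the baseline rules in SAP 3.3 and 4.5.1 prove an inconsistency. The first covers medical conditions present at screening. The second concerns unsolicited events, and it reports temperatures in the 7 days after a dose as solicited events.

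Finally, a pre-dose snapshot cannot remove background symptoms that begin during the 7 days. Without a placebo, no counting rule separates those in the absolute rates.

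**Conclusion.** The point holds for the absolute and per-dose systemic rates in each arm, as a limited gap in the summary tables. Tables 32–34 and the Maximum rows of Tables 35–46 include symptoms that preceded the injection, and no planned summary compares pre- and post-dose grades within a participant. The direction is upward. The size that can be stated from the documents is that of one participant: 0/10 (0–31%) becomes 1/10 (0.3–44.5%). The rates in step 3 rest on an assumed prevalence, full persistence and, for the any-vaccination column, independence across doses; they show a range and are not an estimate.

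The point does not extend to fever or local symptoms, to a material bias in the comparison of ALFQ with CJCV2 alone, or to a claim that dose-to-dose carry-over is common. Nor do the documents support replacing the planned count as the basis for conclusions, since that count matches the endpoint and is cautious for safety.

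**What to change.** Keep the current rows in Tables 32–34. Add a supportive row, new or worsened versus pre-dose, for each systemic symptom other than fever and for Any Systemic Symptom, for each vaccination and for any vaccination.

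- **Definition.** A participant counts if at least one individual symptom has a maximum post-dose grade within 7 days above that same symptom's pre-dose grade at that dose.
- **Any Systemic Symptom.** Apply the definition symptom by symptom, so that a pre-existing mild headache cannot mask new mild nausea. New fever counts toward this row.
- **Footnotes.** State both counting rules, and report both rows with neither replacing the other.

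The cost is SAP text and extra rows; the pre-dose grades are already collected on Days 1, 29 and 57. The downsides are longer tables, and a supportive row that omits a symptom which resolves and then recurs at the same grade. That omission is a further reason to keep the planned row beside it.

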### 14.3.2 Listing of Deaths, Other Serious and Significant Adverse Events

**Table 62: Listing of Serious Adverse Events**

*[Implementation Note: The “Start Day Relative to Vac (Duration)” column will be the day of AE onset with the day of the associated vaccination being Day 1; the duration will be the duration of the AE in days. For the “Reason Reported as an SAE” column, include all reasons selected in the eCRF; if the box for a medically important event not covered by other “serious” criteria is checked, display “Other medically important event: [reason entered by site]”. For “If Not Related, Alternate Etiology”, concatenate the “If Not Related, is event related to” and the “If Not Related, specify alternative etiology” fields from the Adverse Events eCRF separated by a colon. If there are no comments, include “None” in the comments row. In the CSR, Participant ID should be USUBJID (not PATID) for purposes of de-identification. Sort by Treatment Group, Participant ID, and AE Number.*

*If no SAEs are reported, this table will be replaced with text that states, “No Serious Adverse Events have been reported in Protocol 19-0003.” There should be a black border around the text, and the text should be a minimum of 9 pt font.]*

Adverse Event	Associated Vac No.	Start Day Relative to Vac (Duration)	Day Relative to Vac Event Became Serious	Reason Reported as an SAE	Severity	Relationship to Study Vac (If Not Related, Alternate Etiology)	Action Taken with Study Vaccinations	Participant Discontinued Due to AE?	Outcome	MedDRA System Organ Class	MedDRA Preferred Term
Treatment Group: [X] µg [CJCV2 or CJCV2+ALFQ], Participant ID: EHD.XXXXX, AE Number: XXX											
	Vac [X]	Day X (Y Days)	X		[Mild, Moderate, Severe]	[Related, Not Related ([alternate etiology])]		[No, Yes]			
Comments:											
Treatment Group: [X] µg [CJCV2 or CJCV2+ALFQ], Participant ID: EHD.XXXXX, AE Number: XXX											
Comments:											
Notes: Vac = Vaccination; No. = Number; SAE = Serious Adverse Event; AE = Adverse Event; MedDRA = Medical Dictionary for Regulatory Activities.											

